2 STUDY RATIONALE

There is a great need to understand the cognitive processes underlying illicit opioid use during methadone maintenance treatment for opioid use disorder, especially in patients with co-occurring chronic pain. Ongoing use is associated with increased risk for opioid overdose, treatment drop out and HIV seroconversion/transmission.

2.1 Risk / Benefit Assessment

The purpose of the study is to conduct a Phase 1 clinical trial / human laboratory study to examine the effect of chronic pain alone and in presence of acute opioid withdrawal on

Version #: 1.9 Version Date: 12/09/2020 Page 10 of 37

delay discounting of money in patients on methadone maintenance for the treatment of OUD. Additionally, this project will examine how pain catastrophizing may modify the association of chronic pain and opioid withdrawal on changes in delay discounting of money. If withdrawal and catastrophizing were found to affect impulsive decision making as assessed by delay discounting, future research could extend the study of these variables to determine if they play an explicitly causal role in decisions to use opioids (relapse). Delay discounting may then be shown to serve as a surrogate endpoint in clinical trials assessing primary or secondary prevention of opioid use disorders. Researchers could develop interventions to remediate impulsivity as assessed by delay discounting, thereby preventing relapse and improving the efficacy of opioid use disorder treatment.

There are no direct benefits to the research participant. The research has the potential to improve the lives of future patients with opioid use disorder by improving treatment retention and reducing risk for overdose deaths.

The impulsivity tasks and assessments present no risks exceeding those of normal everyday experiences, although participants may experience boredom, fatigue, or frustration during as a result of these sessions and other assessments.

The main potential risk involves precipitated opioid withdrawal. Opioid withdrawal is distressing to the individual, but is not life threatening. Symptoms may include nausea, vomiting, diarrhea or loose stools, body aches, dysphoric mood, and gooseflesh. Changes to vital signs, including elevations in pulse and blood pressure, may also occur. OTOP staff members are well trained to recognize and treat these symptoms.

There is a small risk of worsening psychiatric symptoms or substance relapse while undergoing precipitated withdrawal. All attempts will be made to screen out vulnerable individuals, and to ensure that no symptoms of pain or withdrawal remain at the end of sessions. If relapse does occur, we will communicate this information to the outpatient opioid treatment program. Consent to contact the program to verify the methadone dose is a pre-requisite for study participation. If need be, referrals can be made for psychiatric or higher levels of substance abuse treatment, including emergency room psychiatric care at Zuckerberg San Francisco General Hospital, on the campus where OTOP is located. Suspected psychiatric disorders discovered during screening will be referred for ongoing treatment. If the patient is at OTOP, [name] will provide this service. If at another opioid treatment program, the patient will be referred to a near-by San Francisco mental health treatment provider (Westside Community Service or Dore Urgent Care Center). These clinics offer urgent care, drop-in and ongoing psychiatric treatment for patients regardless of ability to pay. Ancillary, non-opioid medications, and ice packs will also be available to treat residual withdrawal symptoms or pain at end of session.

3 STUDY OBJECTIVES

We hypothesize that the chronic pain group (PAIN) will show greater delay discounting (greater impulsivity) than the group without pain (NO PAIN) in both the control and opioid withdrawal sessions; and that discounting will be greater in the withdrawal session than control session for both groups, with the greatest discounting observed in the PAIN group while in withdrawal.

Version #: 1.9 Version Date: 12/09/2020 Page 11 of 37

We also hypothesize that across PAIN and NO PAIN groups, pain catastrophizing will independently modify the effect of precipitated opioid withdrawal on delay discounting, with higher levels of catastrophizing associated with a stronger association between withdrawal and delay discounting

3.1 Primary Objective

Determine the effect of aversive stressors on delay discounting in persons on methadone maintenance.

3.2 Secondary Objectives

Investigate the degree to which trait pain catastrophizing modifies the association between opioid withdrawal and delay discounting.

4 STUDY DESIGN

4.1 Study Overview

This is an outpatient Phase 1 clinical trial investigating the effect of naloxone precipitated withdrawal on delay discounting. Eligible participants will undergo two experimental sessions presented in random order. One session will involve the measurement of delay discounting 30 minutes after double-blind intramuscular (IM) administration of placebo (normal saline) and the other will have the exact same procedures performed after double-blind IM administration of naloxone (0.1 mg). Injections will occur 2 hours after methadone dosing (peak levels). Study sessions will last 2 hours and involve pain and opioid withdrawal measures assessed at baseline and 15-minute intervals after injections. Sessions will occur at least 48 hours apart.

This is a two-year grant proposal. The first two months will be used for study start-up, the next 20 months for study recruitment and completion of all study visits, and the last two months for data analysis and manuscript preparation. Each participant is expected to participate for 2-4 weeks, depending on scheduling of two sessions.

There are three sites on the campus of Zuckerberg San Francisco General Hospital where activities will take place. (1) Opiate Treatment Outpatient Program (OTOP). Participant recruitment, data collection and storage, and some study visits will take place at OTOP. (2) Unit 5B in Building 5. ECGs during screening and unblinded study medication preparation. (3) Ward 84 in Building 80. Some study sessions may take place at Ward 84. Johns Hopkins University's Behavioral Pharmacology Research Unit (BPRU) will be the site of data analysis. Johns Hopkins will only have access to de-identified human subject data, and so a central IRB is not needed for this study.

5 CRITERIA FOR EVALUATION

5.1 Primary Efficacy Endpoint

Delay discounting for money will be assessed 30 minutes after study medication IM injection in both experimental sessions. Discount rates (k values) will be assessed with a computer program developed by [name], utilized in a variety of previous studies of delay discounting.

Version #: 1.9 Version Date: 12/09/2020 Page 12 of 37

5.2 Secondary Efficacy Endpoints

Secondary outcome variables will include measures of pain and opioid withdrawal, i.e.

- Pain Visual Analog Scale (VAS)
- Clinical Opiate Withdrawal Scale (COWS)
- Subjective Opiate Withdrawal Scale (SOWS)
- Vital Signs
- Pupil Diameter
- VAS Ratings of Subjective Drug Effects

In addition, personality questionnaires assessing impulsivity will be collected at screening and compared across groups, including

- Barratt Impulsivity Scale-11
- · Eysenck Impulsivity Questionnaire
- Sensation Seeking Scale
- Zimbardo Time Perspective Inventory

In addition, pain catastrophizing will be assessed and will be a main predictor variable in the linear regression models assessing effect modification in study Aim 2.

5.3 Safety Evaluations

- Incidence of adverse events
- Change in vital signs from baseline

6 SUBJECT SELECTION

6.1 Study Population

The participants will be adult persons (age 18-65) with opioid use disorder who are currently maintained on a stable methadone maintenance dose. Half (50) of the completers will have chronic pain (PAIN group) and half will be pain free (NO PAIN group). Otherwise, the participants will be healthy enough (as determined by medical history, physical, and EKG) for study entry. Participants will be required to abstain from illicit substances and alcohol throughout the trial.

It is estimated that approximately 200 persons will have an in-person screening to enroll 130 participants on methadone maintenance that meet all inclusion/exclusion criteria. We will need 100 completers to have the necessary power to perform our statistical analysis, 50 persons in the PAIN group and 50 persons in the NO PAIN group.

6.2 Inclusion Criteria

- Male and female adults aged 18-65
- Stable methadone dose (at least 21 days) verified by contacting participant's opioid treatment program
- Understand and speak English
- Urine toxicology screen negative for drugs of abuse and positive for methadone
- Must be without by signs of intoxication as evidenced by ability to receive full dose of methadone prior to research activities

Version #: 1.9 Version Date: 12/09/2020 Page 13 of 37

 Presence of chronic pain (>3 months) for the PAIN group and absence of pain for the NO PAIN group

6.3 Exclusion Criteria

- Unstable psychiatric illness as assessed by the Mini International Neuropsychiatric Interview (e.g. active suicidal ideation, psychosis)
- Unstable medical illness as assessed by the study's independent medical monitor (e.g. uncontrolled hypertension, recent myocardial infarction, recent stroke, unstable angina) that may be affected by precipitated withdrawal
- Prescription opioid use besides methadone
- Acute pain process unrelated to chronic pain
- Women who are pregnant or lactating
- Known allergy to naloxone.

Patients will be allowed to re-screen if it is expected that an inclusion criterion not met or an exclusion criterion met will change prior to the end of study recruitment.

7 CONCURRENT MEDICATIONS

All subjects should be maintained on the same dose of methadone throughout participation in the trial.

7.1 Allowed Medications and Treatments

Ancillary, non-opioid medications, and ice pack will also be available to treat residual withdrawal symptoms or pain at session end.

7.2 Prohibited Medications and Treatments

The following medications are prohibited during the study and administration will be considered a protocol violation.

• Other opioid analgesic agents other than methadone.

8 STUDY MEDICATIONS

8.1 Method of Assigning Subjects to PAIN or NO PAIN Groups

Patients with chronic pain will be identified by self-report and confirmed by history and physical performed by [name] or another qualified study clinician. Pain will be assessed using the miscellaneous pain questionnaire from the National Health and Nutrition Examination Survey (NHANES; (83)), the Widespread Pain Index, and the Brief Pain Inventory. [name] will be consulted on challenging cases to help clarify the presence or absence of chronic pain.

8.2 Blinding

Due to the objectives of the study, the identity of test and control treatments will not be known to investigators, research staff, or participants. The following study procedures will be in place to ensure double-blind administration of study medications.

Version #: 1.9 Version Date: 12/09/2020 Page 14 of 37

- Access to the randomization code will be strictly controlled.
- The volume and color of IM medication administration will be the same for naloxone and placebo
- Packaging and labeling of naloxone and placebo will be identical to maintain the blind.

The study blind will be broken on completion of the clinical study and after the study database has been locked.

The order of sessions with exact study medications will be given to [name] in a sealed envelope and kept in a locked file cabinet. This envelope will be readily available for un-blinding in case of medical emergency. The envelope will be destroyed by [name] after participant has completed study participation.

8.3 Formulation of Naloxone and Placebo

IDS pharmacy staff will be in charge of purchasing study medications (naloxone and placebo (0.9% normal saline)) from commercial sources. The final amount of each injection will be the same, not to exceed 0.5 mL per injection. Unblinded nursing staff on Unit 5B will draw up the study medication and provide to study staff, ensuring packaging and labeling are identical.

8.4 Supply of Study Drug at the Site

IDS pharmacy will order and maintain the supply of all study medications. They will follow all applicable regulations and policies for ordering, procurement, storage, dispensing and destroying unused medication. Study medication will be prepared and provided to [name] staff prior to each session by unblinded Unit 5B nursing staff.

8.4.1 Dosage/Dosage Regimen

Naloxone 0.1 mg will be given via IM injection, preferably in the Deltoid region. The total volume will not exceed 0.5 mL per injection. Naloxone is a MOR antagonist that had FDA approval to be used to reverse opioid toxicity and is routinely used in experimental studies to induced mild opioid withdrawal symptoms (Strain et al., 1995, Strain et al., 1992; Mendelson et al., 1997; Kanof et al., 1991). In addition, one pre-clinical study in female stumptailed macaques maintained on morphine showed 0.1 mg naloxone administration elicited behaviors consistent with mild opioid withdrawal (Grant et al., 1988). Normal saline will be used as placebo and will also be administered via IM injection. The total volume of placebo will be equal to naloxone injection, not to exceed 0.5 mL per injection.

8.4.2 Dispensing

The IDS pharmacy staff will dispense the medications to Unit 5B nursing staff who will then draw up study medication and label to ensure blinding. [name] staff will receive study medication from Unit 5B nursing staff and then administer it in Ward 95 per protocol. If the session is cancelled or rescheduled, study medication will be returned to IDS pharmacy staff for destruction according to all applicable regulations and policies.

Version #: 1.9 Version Date: 12/09/2020 Page 15 of 37

8.4.3 Administration Instructions

Prior to session commencing, participants must give a UDS that is positive for methadone and negative for illicit substances and other prescription opioids. In addition, the participant must not have any signs of intoxication and meet pain parameters described in the inclusion / exclusion criteria. During the COVID-19 pandemic, participants must also screen negative per hospital policy to be allowed into Ward 95 to begin study sessions. Lastly, the participant will smoke 1 cigarette 20 minutes prior to injection. [name] or another qualified and licensed medical clinician will administer the IM injection in the deltoid muscle of the participant. The injection will occur two hours after their daily methadone dose was given.

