9.7 Psychiatric Assessments

The Mini International Neuropsychiatric Interview will be conducted by [name] during screening to rule out persons with suicidal ideation or psychosis. In addition, the following scales will also be measured at Session 1: PHQ-15 (3) which provides a measure of somatization), PHQ-9 (4) which measures depressive symptoms, and GAD-7 (5) which measures anxiety symptoms.

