10 EVALUATIONS BY VISIT

10.1 Visit 1 (Screening)

- 1. Review the study with the subject and obtain written informed consent and HIPAA authorization
- Assign the subject a unique screening number
- 3. Collect urine for urine drug screen (and pregnancy test if female)
- 4. Collect ROI for opioid treatment program
- Record demographics data
- 6. Record medical history
- Record drug use history
- Record concomitant medications

Version #: 1.9 Version Date: 12/09/2020 Page 19 of 37

- 9. Perform a complete physical examination
- 10. Perform and record vital signs
- 11. Perform and record oximetry
- Perform and record EKG
- 13. Perform and record MINI
- 14. Perform and record BPI
- 15. Perform and record NHANES Miscellaneous Pain Questionnaire
- 16. Perform and record Widespread Pain Index
- 17. Perform and record BPI
- 18. Schedule subject for Visit 2 (Session 1) as appropriate.
- 19. Randomize subject

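### The psychiatric exclusion is assessed by the MINI at screening only, and no stated condition for starting a session directly re-checks it before either injection

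*Combined protocol and SAP*

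**What the plan says.** **The exclusion and its instrument.** Section 6.3 of the protocol excludes "Unstable psychiatric illness as assessed by the Mini International Neuropsychiatric Interview (e.g. active suicidal ideation, psychosis". Section 9.7 places the MINI "during screening to rule out persons with suicidal ideation or psychosis". The Visit 1 list in 10.1 has the entry "Perform and record MINI"; the list for Sessions 1 and 2 in 10.2 has no such entry.

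**The conditions on a session day.** Section 8.4.3 asks for a urine screen positive for methadone and negative for illicit drugs and other prescription opioids. It adds that "the participant must not have any signs of intoxication and meet pain parameters described in the inclusion / exclusion criteria" and, during the pandemic, requires a negative COVID-19 screen. Section 9.2.3 requires zero breath alcohol, 9.2.1 a pregnancy test, and 9.6.3 a current-pain score within set limits, failing which the session is moved.

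**The risk.** Section 2.1 states: "There is a small risk of worsening psychiatric symptoms or substance relapse while undergoing precipitated withdrawal". Its preventive step is that "All attempts will be made to screen out vulnerable individuals". It then describes symptom control at the end of the session, referral, and emergency psychiatric care on the same campus.

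**The timing.** Section 10.1 says only "Schedule subject for Visit 2 (Session 1) as appropriate". Section 4.1 says "Each participant is expected to participate for 2-4 weeks, depending on scheduling of two sessions", and the synopsis describes two to four weeks as an average.

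**The concern.** The protocol names psychiatric worsening under precipitated withdrawal as a risk, and the only assessment directed at that risk is made before the participant enters the sessions. Status can change between screening and injection. The protocol accepts this in one direction: 6.3 lets a patient re-screen when an exclusion that is met is expected to lapse. It has no matching step for an exclusion that arises after screening.

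What is at stake is participant safety. A participant who becomes suicidal or psychotic after screening, and in whom general questioning does not bring this out, could satisfy the listed conditions and be injected. Section 2.1 lists dysphoric mood among the possible withdrawal symptoms. Section 1.1 reports that chronic pain during medication assisted treatment is associated with suicide risk, and half of the planned sample is recruited because of chronic pain. The referral and emergency routes in 2.1 act once a problem is recognised; they do not prompt the question before dosing.

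**Working it through.** The protocol gives no figure to reproduce here. The check is to set out every session-day item and ask whether it comes before the injection (10.2 step 8), whether it is a condition for starting, and whether it is directed at psychiatric status.

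| Session-day item | Section | Before injection | Condition or stopping reason | Directed at psychiatric status |
|---|---|---|---|---|
| Urine drug screen | 8.4.3, 9.2.2 | Yes | Yes | No |
| No signs of intoxication | 8.4.3 | Yes | Yes | No |
| Pain parameters, current-pain score | 8.4.3, 9.6.3 | Yes | Yes | No |
| COVID-19 screen | 8.4.3 | Yes | Yes | No |
| Breath alcohol | 9.2.3 | Yes | Yes | No |
| Pregnancy test | 9.2.1, 12.1 | Yes | Yes | No |
| Methadone dose timing | 8.4.3, 10.2 step 5 | Yes | Yes | No |
| Adverse event probe | 10.2 step 1, 11.1 | Yes (step 1) | Only through 12.1 discretion | Not specifically, but not limited to somatic events |
| Medication review | 10.2 step 2 | Yes | Only for prohibited drugs or through discretion | Not specifically, but could show a new psychiatric drug |
| Vital signs, oximetry | 9.1.5, 9.1.6, 10.2 step 6 | Yes | No threshold stated | No |
| PHQ-15, GAD-7, PHQ-9 | 9.7, 10.2 steps 12 to 14 | No, listed after step 8 | No threshold or action stated | Yes, but Session 1 only under 9.7 |

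Of the seven stated conditions or checks (the first seven rows), none is directed at psychiatric status. Two pre-injection items give a partial, non-specific check. The only psychiatric scales in the session list come after the injection and lead to no stated action.

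**Age of the MINI at Session 2.** If Session 2 falls at the end of the expected participation, the MINI is 2 x 7 = 14 to 4 x 7 = 28 days old. This is an illustration only. Sessions need be only 48 hours apart, so the interval can be shorter. The two to four weeks is an average, no maximum from screening is set, and a failed urine screen or a pain-score mismatch can delay a session, so it can also be longer.

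**How often the question would be asked.** The inputs are 130 enrolled and 100 completing both sessions (synopsis, 6.1).

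- Completers: 100 x 2 = 200 injections.
- The other 130 - 100 = 30 have at most one injection each: 200 + 30 = 230.
- Range: 200 to 230, or 130 x 2 = 260 if nobody drops out.

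These figures measure workload. They say nothing about how many people would be affected, and the documents give no rate from which that could be derived.

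**The case against.** The strongest reply is that the plan does not leave psychiatric status unexamined. Section 11.1 has the investigator actively probe for adverse events at every visit, and its definition of an adverse event covers any unfavourable symptom or disease. This and the medication review come before the injection. A qualified, licensed clinician gives the injection. Section 12.1 allows discontinuation whenever the investigator judges it best for the subject, and section 13 makes failure to meet eligibility criteria a violation. The intended withdrawal is mild (8.4.1) and described as not threatening life (2.1), and the psychiatric risk is called small. On this view, screening once and relying on clinical judgement at dosing is a legitimate choice.

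Much of this stands and limits the point. What it does not supply is a question aimed at these symptoms. General probing may or may not reach them, and discretion under 12.1 and section 13 can be used only once someone knows.

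Four stronger readings are tempting, and the documents do not support them:

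- *That psychiatric illness is the one changeable exclusion with no session-day check at all.* The adverse event probe, medication review and discretion apply to it as they do to medical illness.
- *That unstable medical illness is left equally open.* Blood pressure, pulse, respirations, oximetry, medication review and adverse event probing already precede each injection.
- *That no psychiatric safeguard exists anywhere.* The medical monitoring text that the contents list places in section 11, and the study manual cited in 11.1, were not available, so nothing is claimed about them.
- *That the results are compromised.* Nothing here touches the discounting endpoint, the model or the power.

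**Conclusion.** The point holds in a limited form. In the available text, the psychiatric exclusion is assessed by the MINI at screening only, and the conditions for starting a session contain no directed re-check before either injection. Existing procedures cover the gap in part and non-specifically, and the Session 1 scales cannot gate dosing.

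Its size is modest. The protocol itself rates the risk as small, and the number affected cannot be derived. It is a safety improvement worth making because it is cheap, and it has no bearing on validity, power or analysis. The conclusion assumes that the order of steps in 10.2 reflects the order of conduct and that the unavailable monitoring text and study manual do not already contain such a check. If either of those does, 8.4.3 needs only a cross-reference.

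**What to change.** Add to 8.4.3, as part of the existing pre-injection adverse event probe (10.2 step 1):

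> Before each of the two injections the clinician asks directly, in the same words at both sessions, about current suicidal ideation and psychotic symptoms, and records the answer. If either is present, no injection is given; the session is rescheduled or the participant is withdrawn under 12.1, and the referral route in 2.1 is used.

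Because the injection is blinded, the question has to be asked at both sessions. Identical wording and position keep it balanced across conditions, so the within-subject comparison is not disturbed. No separate medical re-certification is needed. The PHQ-9 and GAD-7 can stay where they are, as variables for the analyses in 14.4.

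**Cost.** A short paragraph and one scripted question, with no new instrument, staff or visit. Assuming 3 to 5 minutes per check (the documents give no figure), the total is 200 x 3 / 60 = 10.0 hours to 230 x 5 / 60 = 19.2 hours over the whole study, and 260 x 5 / 60 = 21.7 hours at most if nobody drops out. The downsides are a few minutes per session, which must fit within the two hours between methadone dosing and injection, and an occasional rescheduled session.
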